3. **Research Plan:** Summarize the study design and research procedures using non-technical language that can be readily understood by someone outside the discipline. **Be sure to distinguish between standard of care vs. research procedures when applicable, and include any flowcharts of visits specifying their individual times and lengths.** Describe the setting in which the research will take place.

1. Study Design and Overview

Ninety treatment seeking men and women with AUD will be recruited to participate in and complete this preliminary study. Participants will be recruited through flyers and advertisements in local newspapers and from community substance abuse treatment facilities. Subjects will participate in an initial screening and intake session to obtain informed consent, followed by physical examination and blood work to determine eligibility. Eligible

participants will be randomly assigned to 2 doses of PREG (300/500 mg/day) vs placebo (PLA) treatment (N=30/group) over 8 weeks. In week 2, AUD patients will participate in a 3day human laboratory study where they will be exposed to three experimental sessions of stress, alcohol cue and neutral-relaxing imagery on separate days (Fox et al.,2007; 2009; Sinha et al., 2008; 2009; 2011). Throughout the study, participants will come twice-weekly to the Yale Stress Center to receive medication, counseling and provide urine samples for UTOX. Women will be enrolled during the mid-luteal phase of the menstrual cycle so that laboratory sessions will be scheduled during the early to mid-follicular phase of the cycle when endogenous sex hormone levels are low prior to ovulation. PREG doses and matching placebo will be obtained by Yale IDS for compounding and dosing to 300mg and 500mg of PREG or PLA. Participants will self-administer study medication on a twice-daily dosing schedule throughout entire study.

Subjects will begin with full respective dose of medication immediately without a titration period, as previous studies with similar doses of pregnenolone up to 500 mg/day at b.i.d. dosing to be well tolerated and with no side effects (Marx et. al., 2009; Marx et al., 2014; Brown et al., 2014; Sripada et al., 2013).

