Once a subject is deemed eligible, signs consent and completes all intake assessments, s/he will be randomized to 300mg PREG, 500mg PREG, or PLA and exposed to three laboratory sessions as close together as possible of guided imagery of stress, drug cues and neutral-relaxing cues in week 2 (identified as lab DAY 1, DAY 2, and DAY 3). In a session prior to laboratory sessions, subjects will participate in an imagery script development to provide descriptions of recent stressful, drug cue related and neutral relaxing situations to the research assistant. On the day before laboratory session 1 , subjects will participate in a relaxation and imagery training and IV habituation session, followed by three laboratory sessions that include IV blood drawing.

Daily surveys using a Smartphone platform (MetricWire) monitoring will prompt subjects to take study medication, and provide responses on their alcohol use, craving, stress and mood states for the day (see below for detailed description).

Genetic studies:

Ten mL of whole blood will be collected during physical examination to assess eligibility, and thirty-two mL of whole blood will be also collected from patients on the day of the first laboratory session (LAB DAY 1) for the purposes of understanding genetic factors that may affect craving.

Throughout the 8 week study, subjects will self-administer 300mg/day, 500mg/day or PLA/day and study staff will provide weekly medication packs to subjects.

Participants will be seen twice per week at the Yale Stress Center at [name] to receive once/week counseling, provide urine and receive contingency management for treatment attendance. Daily surveys using the smartphone platform (MetricWire) monitoring will prompt subjects to take study medication, and provide responses on their alcohol use, craving, stress and mood states for the day. Smartphone data will be collected daily. Subjects will be prompted at two random times in the morning and afternoon to complete a brief 1-minute survey of questions and a third 5-10 minute survey to be completed at night before bedtime. The surveys are set up with standard automated questions and prompts and subjects will use the smartphone key pad to answer the prompts (via MetricWire).

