Medication compliance will also be monitored through the use of riboflavin as a marker. Riboflavin produces a bright yellow discoloration of the urine when the medication is taken 2 to 8 hours prior. During the study, staff will easily be able to visually inspect the subject's urine to determine whether the morning dose has been taken. 25mg of riboflavin will be added to all doses of pregnenolone and placebo by the pharmacist when capsules are made. Medication compliance will also be implemented through video Directly Observed Therapy (DOT) using the smartphone application eMocha. Subjects will use the eMocha app to video record themselves taking their medication. Research staff will log into a secure site to view the recorded videos to assess medication dose adherence.

Individual Counseling:

Subjects will participate in once weekly standard individual drug counseling as outlined in the Individual Drug Counseling Manual (IDC, Mercer & Woody, 1994) during the treatment phase in order to support treatment. Each subject will be seen by a Yale Stress Center staff counselor with expertise in IDC who will see the patient for the clinical component of the treatment research phase. The general purpose of the counseling sessions as described in the manual are to: (1) acquire information about important concepts and aspects of recovery from addiction; (2) increase self-awareness of specific problems and issues in relation to addiction and recovery, and (3) learn new coping skills to deal with problems contributing to or resulting from the addiction and to improve functioning. The focus of this psycho-educational approach is on providing patients with frequent supportive contact, introduce them to key concepts about the recovery approach, and develop a sense of personal responsibility for recovery.

**Participants will provide urines 2x/week to assess drug use, and they will receive contingency management for showing up on each of the twice/weekly appointments. Primary outcomes measures will be alcohol use, mood, stress and craving as assessed by MetricWire and urines.

After completion of the study, subjects will be referred to aftercare at the Substance Abuse Treatment Unit (SATU).

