Reporting of Other Study-Safety Events: The project PI will inform the Data Safety Monitor, the Yale HIC, NIDA project officer and the sponsor promptly of any change in recruitment or other changes in this project that are relevant to safety, as well as any action taken by the Yale HIC as a result of continuing review of this project.

12. Statistical Considerations: Describe the statistical analyses that support the study design. For this preliminary study data we will mostly use descriptive statistics for comparing the medication groups on primary outcome measures and safety measures. Repeated measures ANOVA and mixed model procedures to assess treatment group differences in alcohol craving and stress related arousal (heart rate, blood pressure, HPA and catecholamine responses) during laboratory exposure to stress and drug cues as compared to neutral imagery conditions. Non-parametric tests will be used to assess occurrence of side effects, alcohol use measures, CIWA scores and perceived stress scores during the treatment study phase. The number and type of AE's for the two medication groups will be conducted using t-tests, chisquare tests and ANOVAs as appropriate. Findings will be used to estimate effect sizes for the medication and guide the larger randomized clinical trial in the future.

Primary Outcome Measures during 8 week treatment: The primary outcome measures will be:(1) alcohol use as measured by weekly urine drug screens and self-report of drug use on the Substance Use Calendar, (2) side effects and adverse events as measured by the SAFTEE, and (3) treatment adherence as measured by frequency of attendance for medication selfadministration and attendance for counseling appointments, including missed sessions.

Secondary Outcome Measures: Secondary outcome measures will include alcohol craving scales, alcohol withdrawal assessment using the CIWA, perceived stress scale, the recent stressful life events scale (LES), and the COPE Questionnaire. In addition, other assessments will be used to ensure that medications groups are not different in various measures at baseline and also to assess their role in predicting treatment response. Examples of such

assessments would be demographic measures, depressive and anxiety symptoms, motivation to change and thoughts about abstinence, which are measures that have been found to predict substance abuse treatment outcomes (Hall et al., 1990; 1991; McMahon et al., 1986).

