We selected 300mg and 500 mg/day versus placebo dosing based on prior clinical trials of pregnenolone in psychiatric patients (men and women). In an 8-week clinical trial in schizophrenia patients, fixed escalating dosing from 100mg to 500mg of pregnenolone (Marx et al., 2009) was well tolerated. The only side effects present in the pregnenolone group to a greater degree than the placebo group were two reports of mild restlessness, one report of mild muscle pain/stiffness, and one report of mild cold extremities. A follow-up randomized clinical trial in men and women with schizophrenia used escalating doses of pregnenolone, 100mg for 2 weeks, 300mg for 2 weeks, 500mg for 4 weeks, and found pregnenolone to be safe and well tolerated (Marx et al., 2014). A 12-week randomized placebo-controlled trial of escalating doses of pregnenolone to 400mg daily for 4 weeks in men and women with bipolar depression improved depressive symptoms and showed pregnenolone to be safe and well tolerated in all patients (Brown et al., 2014). A recent study using an acute dose of pregnenolone of 400mg to examine the effects of ALLO its effects on emotion regulation neurocircuitry (Sripada et al., 2013), also didn't find any side effects.

3. Source: a) Identify the source of the drug or biologic to be used.

Medication Administration and Compliance: Pregnenolone and matching placebo pills will be provided by Yale IDS Pharmacy who will make up identical active and placebo capsules, packaged into weekly packs for medication self-administration. Subjects will be randomly assigned to twice daily dosing of 300mg and 500mg PREG/PLA. Subjects will selfadminister study medication twice daily. Study staff will monitor vital signs and side effects during bi-weekly face-to-face appointments. We expect all subjects to tolerate doses of 300mg and 500mg pregnenolone. Alcohol craving, abstinence symptoms, mood and perceived stress scale and side effects will be assessed twice weekly. Urines will be obtained twice weekly.

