Medication compliance will be monitored by blood draws done at weeks 2, 5, and 7, to measure PREG levels, and through the monitoring of riboflavin as a urine marker. Riboflavin produces a bright yellow discoloration of the urine when the medication is taken 2 to 8 hours prior. Subjects will be taking morning and bedtimes doses of the medication. After this time, staff will easily be able to visually inspect the subject's urine to determine whether the morning dose has been taken. 25mg of riboflavin will be added to all doses of PREG and PLA by the pharmacist when capsules are made.

Subjects will self-administer study medication, and will be reminded via daily smartphone platform monitoring. Daily smartphone monitoring will be used to prompt patients to take study medication, and also to assess alcohol use, craving, craving resistance and mood states. Concordance between daily smartphone reports and alcohol positive urines will be evaluated for daily versus retrospective reporting.

Medication compliance will also be implemented through video Directly Observed Therapy (DOT) using the smartphone application eMocha. Subjects will use the eMocha app to video record themselves taking their medication. Research staff will log into a secure site to view the recorded videos to assess medication dose adherence.

All participants and study staff will remain blind to medication condition.

b) Is the drug provided free of charge to subjects? Yes No If yes, by whom?

4. Storage, Preparation and Use: Describe the method of storage, preparation, stability information, and for parenteral products, method of sterilization and method of testing sterility and pyrogenicity.

Commercially available pregnenolone and matching placebo will be obtained, formulated and packaged by Yale IDS Pharmacy in weekly bubble packs for self administration by subjects. Medication and placebo be stored at the Yale Stress Center in our designated medication room in a locked cabinet. Access will be provided to the research nurse, [name], the study physician, [name], and study PI and Co-I, [name] and [name]. Self-administration and dispensing will be conducted by the research nurse or coordinator.

Check applicable Investigational Drug Service	utilized:
 YNHH IDS	 Yale Cancer Center
 CMHC Pharmacy	 West Haven VA
 PET Center	
 Other:	
	None

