2. Payments for Participation (Economic Considerations): Describe any payments that will be made to subjects, the amount and schedule of payments, and the conditions for receiving this compensation.

Subjects completing the Study will receive \$20 for a remote intake interview session or \$25 for an in-person intake interview session, \$25 for the imagery and relaxation training session, and \$100 for each of the 3 laboratory sessions. Subjects will also be paid a \$50 bonus for completing the laboratory sessions. Therefore, for the completion of all procedures leading up to and including the laboratory sessions, subjects will receive up to a total of \$400.

If subjects continue on to complete the treatment phase, they will earn chances to win dollar prizes for kept appointments to encourage appointment attendance. For every twice/weekly appointments they attend, the chance to draw a prize from the fishbowl will increase by one. The fishbowl prizes are in increments of \$1, \$5, \$20, and \$100. Subjects will participate in this at every twice/weekly appointment they attend. If they miss any appointment, or fail to take study medication, the chances will be reset back to one. For example, if no appointments are missed the subject will have a total of 8 chances at the last appointment. Each prize increment that is won from the 8 attempts is then added together into a lump sum. There is no limit on the amounts that can be won. A standard payment rate of \$20 per week can be used in lieu of drawing from the fish bowl in order to encourage completion of appointments.

Subjects participating in smartphone monitoring will be compensated for their participation at \$2 a day, with a \$6 bonus for completing all 7 days, hence a possible total of \$20 a week, or \$160 for all 8 weeks of the study. Subjects will receive \$25 per week for taking study medication using eMocha for a total of \$200 for completing all 8 weeks. In addition, subjects will receive \$25 for week 3, \$25 for week 5, \$25 for week 7, and a \$25 bonus for completing the treatment phase. The total that subjects may be reimbursed if they complete all aspects of the study will be \$860 plus the various amounts won for keeping appointments during the treatment phase.

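### The primary adherence outcome counts attendance, but capsules are self-administered from weekly packs, so it reports retention and sees at most about 14% to 21% of scheduled doses

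*Combined protocol and SAP*

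**What the plan says.** Section V.12 (Primary Outcome Measures during 8 week treatment) lists three primary outcomes: alcohol use, side effects and adverse events, and "treatment adherence as measured by frequency of attendance for medication selfadministration and attendance for counseling appointments, including missed sessions". It gives no denominator, scoring rule or threshold for the third.

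The dosing arrangement is described elsewhere:

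- **Supply.** Section V.3 says that "study staff will provide weekly medication packs to subjects". Section VI.A.3 says the capsules are "packaged into weekly packs for medication self-administration".
- **Frequency and timing.** Section V.3 (Study Design and Overview): "Participants will self-administer study medication on a twice-daily dosing schedule throughout entire study". Section VI.A.3: "Subjects will be taking morning and bedtimes doses of the medication".
- **Duration.** Section V.3: "Throughout the 8 week study, subjects will self-administer 300mg/day, 500mg/day or PLA/day".
- **Visits.** Section V.3 has participants attending twice a week, with counseling once a week.

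Three measures of actual intake are planned in Sections V.3 and VI.A.3. The first is video: "Subjects will use the eMocha app to video record themselves taking their medication", and staff review the recordings to judge dose adherence. The second is riboflavin, added to active and placebo doses and checked by urine color. The third is plasma pregnenolone. None of the three is named in Section V.12.

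**The concern.** The definition reads as if doses were taken at attended visits. With weekly packs and morning and bedtime dosing, most doses fall away from any visit, and a count of kept appointments says little about them. What it does measure is retention.

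This matters in this trial for two reasons. First, Hypotheses 2a, 3a and 3b are dose-dependent across placebo, 300 mg/day and 500 mg/day, so realized exposure bears directly on their interpretation. Second, Section V.12 says the findings will be used to estimate effect sizes and guide a larger trial. An adherence figure that is really a retention figure would mislead whoever plans that trial. Attendance is also rewarded in its own right: Section X.2 says of participants that "they will earn chances to win dollar prizes for kept appointments to encourage appointment attendance".

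**Working it through.** The plan states no adherence figure, so there is none to reproduce. The check counts from its own schedule.

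**Inputs**
- Treatment length: 8 weeks (Section V.3).
- Doses per day: 2 (Sections V.3 and VI.A.3).
- Visits per week: 2 (Section V.3). Section V.10 (vital signs) and Section VIII (urine and breath samples) instead speak of 3 per week.
- Counseling sessions per week: 1 (Section V.3).

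**Counts**
- Scheduled doses: 8 × 7 × 2 = 112.
- Visits at two a week: 8 × 2 = 16. At three a week: 8 × 3 = 24.
- Counseling sessions: 8 × 1 = 8.

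**Largest share of doses that attendance could observe**, assuming one dose is taken in front of staff at every visit, which Section V.12 does not require:
- Two visits a week: 16/112 = 14.3%, leaving 96/112 = 85.7% unobserved.
- Three contacts a week: 24/112 = 21.4%, leaving 88/112 = 78.6% unobserved.
- Two visits a week plus the three laboratory days, if these fall on separate days: 19/112 = 17.0%.

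**How far attendance and intake can diverge**, scoring attendance as attended/scheduled (an illustration, since the plan sets no rule):

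| Participant | Visit attendance | Doses taken |
|---|---|---|
| Keeps every visit, takes half the capsules | 16/16 = 100% | 56/112 = 50% |
| Keeps every visit, takes no capsules | 16/16 = 100% | 0/112 = 0% |
| Misses one of the two visits each week, takes every capsule | 8/16 = 50% | 112/112 = 100% |

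The measure can err in either direction.

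**Link to the dose hypotheses.** A participant in the 500 mg/day arm who takes half the capsules averages 0.5 × 500 = 250 mg/day, below the nominal 300 mg/day arm. Attendance would not show this.

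**The case against.** The strongest reply is that intake is measured, and measured well, so little is lost. Much of this stands. A reader might infer that a null result could not be told apart from non-adherence. The documents do not support that: video, riboflavin and plasma pregnenolone are all collected, pregnenolone and allopregnanolone are assayed in the laboratory sessions, and Aims 2b and 3b use allopregnanolone as a mediator. A null result could be examined against these data. What is missing is a prespecified link from the intake measures to the outcome or to any analysis.

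Other parts of the reply:

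- **Treatment adherence is broader than capsule-taking.** This stands. Participants also receive counseling, so attendance is a legitimate component. It cannot stand in for the medication component, which the definition also claims to cover.
- **Dosing is rewarded too.** This stands. Section X.2 resets the prize chances when medication is not taken and pays $25 a week for doses recorded by video. It would be wrong to say that only attendance is rewarded. These rules govern payment, though, not the outcome score.
- **Tolerability is captured elsewhere.** This stands. The side-effect instrument is itself a primary outcome, so the point should not be read as saying that tolerability goes unseen.
- **Dosing may be supervised.** Section VI.A.4 says that the nurse or coordinator conducts self-administration as well as dispensing. If a swallowed dose were needed for a visit to count, a participant taking no capsules could not score 100%. Section V.12 sets no such condition, and the 14% to 21% ceiling would still apply.
- **The trial is preliminary and mainly descriptive.** This is true, and no hypothesis tests adherence. It limits the consequence but does not justify a primary outcome whose label does not match its content.

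**Conclusion.** The concern holds in a limited form. As written, the primary adherence outcome measures attendance and would present retention as medication adherence. It can directly observe at most about 14% of the 112 scheduled doses with two visits a week, or 21% with three contacts a week. Better intake data are already planned but enter no prespecified analysis.

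This rests on three assumptions: twice-daily dosing for the full 8 weeks, no more than one observed dose per visit, and most doses being taken away from the clinic. The last is inferred from the weekly packs, bedtime doses and self-recorded video; it is not stated outright. The 100% scores in the table are illustrations, because the plan gives no scoring rule. The documents do not support the reading that intake goes unmeasured.

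**What to change.** In Section V.12, split the third primary outcome in two:

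1. **Medication adherence:** video-verified doses divided by 112 scheduled doses, for every randomized participant and summarized by arm. Use riboflavin as a supporting check in all arms, noting that it reflects the morning dose only. Use plasma pregnenolone as a supporting check in the active arms; it says little about capsule-taking on placebo.
2. **Treatment attendance/retention:** visit attendance and counseling attendance, each reported separately.

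State how the adherence measure will be used when the dose-dependent hypotheses are interpreted.

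The cost is mainly analysis wording, with no new procedure. There are two downsides. Doses taken but not filmed count as unverified, so self-reported doses should be reported alongside. Video may also not exist for every participant for the whole period: the documents do not say when it was introduced, and the cited paper on video-observed therapy (2019) postdates the planned July 2018 start. Periods without video available should therefore be treated as missing, not as zero doses, and their extent reported by arm.

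Three sets of statements also need reconciling:
- the outcome's reference to attending for self-administration, and the Section VI.A.4 statement on staff conducting it, with the weekly-pack supply;
- the twice-weekly contacts in Section V.3 with the three-times-weekly contacts in Sections V.10 and VIII;
- the blood-draw weeks for pregnenolone, given as 2 or 5 and 7 in Section V.3 but as 2, 5 and 7 in Sections V.9 and VI.A.3.

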The Substance Use Calendar was developed by Miller and DelBoca (1994) and is based on the Time-Line Follow-Back Method (TLFB) (Sobell, Maisto et al. 1980). The SUC uses a calendar prompt and a number of other memory aids (e.g., holiday, payday, and other personally relevant dates) to facilitate accurate recall of daily drug use during the targeted period. It has demonstrated adequate levels of reliability and validity when administered as an in-person interview, over the telephone, and when administered via computer (e.g. Carey, 1997; Sobell, Brown, Leo, & Sobell, 1996; Sobell, Sobell, Leo & Cancilla, 1988). Its reliability and validity in drug abusing samples has also been established (Fals-Stewart, et al., 2000). In the current study we will use to obtain self-report of day to day use of alcohol, and other drugs, for the 90 days prior to treatment and weekly during treatment.

The Smoking History Questionnaire will be given to collect information on current and past smoking habits. The questionnaire also questions the subject's number of past quit attempts, their perception of health risks, and perceived barriers to quitting.

Fagerstrom Test for Nicotine Dependence (FTND: Fagerstrom, 1978) is a 6-item questionnaire for assessing tobacco dependence, which evaluates, among other factors, depth of inhalation, time from awakening to day's first cigarette, and difficulty in smoking cessation.

The Alcohol Use Disorders Identification Test (AUDIT) (Bohn et al., 1995) is a 10-item screening tool developed by the World Health Organization (WHO) to assess alcohol consumption, drinking behaviors, and alcohol-related problems.

Alcohol Dependence Scale (ADS) is a 25 item to measure severity of alcohol dependence.

Abstinence Measures:

Clinical Institute Withdrawal Assessment (CIWA) is a 13 item scale that measures alcohol withdrawal signs and symptoms. The assessment will be administered weekly and at followup interviews.

Cocaine Selective Severity Assessment (CSSA) is an 18-item scale that measures the cocaine withdrawal signs and symptoms within the past 24 hours. The CSSA will be used weekly and at the follow-up interview.

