Data Analytic Procedures: Since patients will be randomly assigned to the pregnenolone doses and placebo treatment groups, we do not expect the groups to be different on demographic, prior drug use history or other predictor variables. Nevertheless, prior to undertaking the specific analyses, we will compare the treatment groups on demographic variables, substance use characteristics and previous psychiatric history/predictor variables using t-tests/chi-square analyses as appropriate. If any group differences are found, the specific variable will be entered as a covariate in all of the specific analyses.

The laboratory study component proposes a 3 X 2 X 3 mixed-factorial design with Treatment (300mg Pregnenolone vs. 500mg Pregnenolone vs. Placebo) and Sex (AUD women vs. men) as the Between-Subjects factors and Imagery Condition (Stress, Drug Cues and Neutral cues) X Time Period 7 (Baseline, Image, Recovery 1, recovery 2, recovery3, Recovery 4 and Recovery 5) as the Within-Subjects factors. Order of imagery conditions will be randomly assigned and counterbalanced across subjects. As measurements for imagery condition and time period will be repeated within subjects, these are not independent, leading to correlations between measurements. Mixed linear models provide a way not only to model the mean differences between levels of factors, but also allows for modeling of the variancecovariance matrices (Laird and Ware 1982) (Littell, Milliken et al. 1996). This is particularly advantageous for designs such as the one proposed here which require repeated laboratory measurements within subjects. Furthermore, these models also have the capacity to handle missing data, without excluding subjects with missing data points (Cnaan et al., 1997; Littell et al., 1996).

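### Adjusting the Hypothesis 3a comparison for pre-treatment drinking is left to a chance baseline difference, which gives up precision if prior drinking predicts outcome

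*Combined protocol and SAP*

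**What the plan says.** **The rule.** Section V.12, Data Analytic Procedures, tests the arms against each other on demographics, substance use characteristics and psychiatric history or predictor variables, by t-test or chi-square. It then states: "If any group differences are found, the specific variable will be entered as a covariate in all of the specific analyses". No threshold for a difference is given. The same paragraph says "we do not expect the groups to be different on demographic, prior drug use history or other predictor variables".

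**The baseline data.** Section V.3, Substance Use Calendar, collects "self-report of day to day use of alcohol, and other drugs, for the 90 days prior to treatment and weekly during treatment".

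**The outcomes.** Hypothesis 3a names three primary drinking outcomes over the 8 weeks: abstinent days, heavy drinking days and amount of alcohol.

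**The outcome source** is stated in two ways:
- Section V.3, Individual Counseling: "Primary outcomes measures will be alcohol use, mood, stress and craving as assessed by MetricWire and urines".
- Section V.12, Primary Outcome Measures: "alcohol use as measured by weekly urine drug screens and self-report of drug use on the Substance Use Calendar".

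Section V.3, General Procedures, describes the smartphone surveys as part of the 8-week study: "Daily surveys using the smartphone platform (MetricWire) monitoring will prompt subjects to take study medication, and provide responses on their alcohol use". The calendar is therefore the only day-by-day record of pre-treatment drinking that the plan describes.

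**The method** is also stated in two ways. Section V.12 opens with "we will mostly use descriptive statistics for comparing the medication groups on primary outcome measures and safety measures" and continues "Non-parametric tests will be used to assess occurrence of side effects, alcohol use measures". Data Analytic Procedures instead assigns mixed linear models to every aim, with sex, imagery condition and time period listed as fixed effects, and a Cox model to time to relapse. None of these texts names pre-treatment drinking as a covariate. Baseline variables otherwise appear only in balance checks and in prediction analyses that are separate from the treatment contrast.

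**The concern.** When arms are randomized, a baseline difference is due to chance. A test of that difference says nothing about whether the variable predicts outcome, yet prediction is what makes a covariate worth having. The rule therefore selects covariates on the wrong criterion. The obvious candidate, prior drinking, enters only when the arms happen to differ, and the plan itself expects that they will not.

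What is at stake is the width of the intervals around the drinking effects. Section V.12 says the effect sizes will inform a later, larger trial, so their precision matters even though the present comparisons are mostly descriptive. Under the rule, chance also decides whether the reported effect is adjusted at all.

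**Working it through.** The plan gives no alpha, standard deviation, effect size or sample-size derivation, so there is no figure of its own to reproduce.

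**Inputs.** From Section V.3, Study Design and Overview: three arms of 30. Assumed: a baseline-test alpha of 0.05 or 0.10; normal data with outcome SD 1; a baseline-outcome correlation r from 0.1 to 0.7. Baseline tests are either one three-group F test or all three pairwise t-tests. Either one or three drinking measures can trigger the rule, with between-measure correlation 0, 0.5 or 0.8. Simulation: 120,000 trials per cell, common-slope ANCOVA, one dose-placebo difference. The rule enters every flagged measure; the alternative always enters the matching one.

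**Step 1: how often baseline drinking stays out.**

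| Measures that can trigger | Test | Alpha 0.05 | Alpha 0.10 |
|---|---|---|---|
| One | F | 95.0% | 90.0% |
| One | Pairwise t | 87.8% | 77.4% |
| Any of three | F | 85.8-89.9% | 72.9-81.0% |
| Any of three | Pairwise t | 67.7-77.4% | 46.3-61.2% |

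For uncorrelated measures the pairwise entries can be checked by hand: 0.878³ = 0.677 and 0.774³ = 0.464.

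**Step 2: precision.** The unadjusted variance of a dose-placebo difference is 2/30 = 0.0667 (SD 0.258). Always adjusting gives approximately (1 − r²) × 2/30. At r = 0.5 that is 0.75 × 0.0667 = 0.050, SD 0.224; the simulation gives 0.225. Under the rule, the simulated SD at r = 0.5 is 0.243-0.253 (alpha 0.05) or 0.238-0.249 (alpha 0.10). The variance cut from always adjusting, compared with the rule, as minimum to maximum over the cases in Step 1:

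| Assumed r | Alpha 0.05 | Alpha 0.10 |
|---|---|---|
| 0.1 | −0.1 to 0.8% | −0.2 to 1.2% |
| 0.2 | 1.9 to 3.0% | 1.3 to 2.8% |
| 0.3 | 4.5 to 6.9% | 3.4 to 5.8% |
| 0.5 | 14.8 to 21.0% | 10.8 to 18.4% |
| 0.7 | 33.9 to 43.2% | 26.2 to 39.1% |

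**Step 3: in familiar units, alpha 0.05.**
- r = 0.5: 30/(1 − 0.148) = 35 to 30/(1 − 0.210) = 38 effective participants per arm. The 95% half-width is 1.96 × 0.225 = 0.44 SD, against 1.96 × 0.243 = 0.48 to 1.96 × 0.253 = 0.50 SD under the rule.
- r = 0.3: 30/(1 − 0.045) = 31 to 30/(1 − 0.069) = 32 per arm.

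**Step 4: validity of the rule.** In a separate simulation with no treatment effect (one measure, pairwise tests, 20,000 trials per setting), test-then-adjust rejected in 4.9%, 4.1% and 3.3% of trials at r = 0.3, 0.5 and 0.7. It errs toward caution.

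**Step 5: the other named methods (illustrations only).**
- Ranks: assumed skewed abstinent days out of 56, two arms of 30, an illustrative effect. Rank-sum against rank ANCOVA rejected in 58.7% and 58.6% at r = 0.14, 58.4% and 61.4% at r = 0.30, and 58.6% and 70.5% at r = 0.50. Null rejection was 4.8-5.3% for both.
- Cox: two arms of 30, assumed log hazard ratio −0.7. At r = 0.5, power was 43% unadjusted and 60% adjusted, the mean log hazard ratio −0.56 and −0.71, and the standard error 0.314 and 0.324. At r = 0.1, power was 63% and 64%. Any gain is in power, not a narrower interval, and the adjusted hazard ratio estimates a different, conditional quantity.

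**The case against.** **This is a preliminary, mostly descriptive study with no confirmatory test or power target.** True, and it keeps the severity low. It does not dispose of the point, because the plan says its effect sizes will guide a larger trial and an unused covariate widens their intervals.

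**The correlation is unknown.** This stands. At r of 0.1 or less there is no useful gain, and at 0.3 it is one or two participants per arm. All participants receive weekly counseling, which could weaken the link between prior and on-treatment drinking. The correlation may also be lower if the smartphone surveys, rather than the calendar, supply the outcome. Nothing in the documents places r near 0.5. Against that, pre-specifying one covariate costs almost nothing when r is small (a variance change of about −0.2% at worst).

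**The rule does adjust, and not always rarely.** Partly stands. A reader might infer that pre-treatment drinking is nearly always excluded. That fits a single measure, but the plan's list of substance use characteristics is open-ended. With any of three measures tested pairwise at 0.10, all stay out in only 46-61% of trials. Five uncorrelated measures would give 0.878⁵ = 52% at 0.05 and 0.774⁵ = 28% at 0.10, although measures taken from one calendar are unlikely to be uncorrelated.

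**The variance figures come from normal-data ANCOVA, whereas the plan also names rank tests and leaves the treatment-phase model unwritten.** This stands as a limit on the figures. The rank check points the same way, but it rests on assumed data.

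**Conclusion.** The plan leaves adjustment for pre-treatment drinking in the Hypothesis 3a comparison to chance, and no text pre-specifies it, although 90 days of daily use are already collected. For a single matching measure, omission runs at 88-95% (assumed alpha 0.05) or 77-90% (0.10), and it can fall to about half when several measures can trigger the rule. At alpha 0.05, always adjusting would cut the variance by about 0% at r = 0.1, 5-7% at 0.3 and 15-21% at 0.5. Both alpha and r are assumptions.

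Two stronger readings are not supported. A reader might infer that test-then-adjust biases the effect or inflates false positives. The trigger depends only on a chance difference that can fall either way, and the simulated null rejection was at or below 5%. A reader might also infer that the trial misses its power for want of the covariate, but the plan states no power target. This is a low-severity precision improvement, not the repair of an invalid analysis.

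**What to change.** 1. In Section V.12, Data Analytic Procedures, replace the test-then-adjust sentence with descriptive baseline comparisons.
2. For each Hypothesis 3a drinking outcome, write a treatment-phase analysis with treatment, sex and the matching 90-day calendar measure, expressed per day, whatever the baseline comparison shows.
3. If the rank-based tests are kept for skewed day counts, use rank ANCOVA or report the adjusted model beside them.
4. Add baseline drinking to the Cox model once the relapse event is defined, and state that the hazard ratio is conditional on it.
5. So that the model can be written, reconcile Section V.3 (Individual Counseling) with Section V.12 (Primary Outcome Measures) on the outcome source, and the opening of Section V.12 with Data Analytic Procedures on the method.

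**Cost.** Wording only for abstinent days. Heavy drinking days and amount both need daily quantity, and the calendar description mentions only day-to-day use, so first confirm that quantity is recorded. The Cox change needs an event definition that the plan does not contain. No participant procedure changes.
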